1.1. THE IMPACT MODEL

The model, based on MRI parameters, stratifies patients with an incidental meningioma into three risk groups: low-, medium- and high-risk. These MRI parameters are as follows: meningioma volume, meningioma hyperintensity, peritumoral signal change and proximity to critical neurovascular structures. This predictive function was built using an internally validated cox regression model. Patients were also stratified in the model based on age, comorbidity and performance status using competing risk analyses.

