3.5. Study endpoints

3.5.1. Primary endpoint

Disease progression will be defined using a composite endpoint comprising of new symptom development, meningioma-specific mortality, meningioma growth (absolute growth rate ≥ 2 cm³/year or absolute growth rate ≥ 1 cm³/year + relative growth rate $\geq 30\%$ /year), development or increase of peritumoural brain oedema (defined as increased signal intensity on T2/FLAIR), venous sinus invasion and meningioma volume exceeding 10 cm³. The first two criteria denote clinical progression while the latter three are related to loss of window of curability. Venous sinus invasion and peritumoural oedema can prevent complete surgical resection (13, 14). Peritumoural oedema and a meningioma volume >10 cm³ are relative contraindications to stereotactic radiosurgery (15, 16).

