3.8.2. Baseline radiological variables

Baseline imaging variables assessed will be:

- Single or multiple intracranial meningioma
- Tumour signal intensity compared to the contralateral grey matter on fluid attenuated inversion recovery (FLAIR) and T2-weighted (T2) MRI (hypo/iso/hyper) (Figure 2)
- Peritumoural signal intensity in relation to tumour volume using the signal change present on FLAIR and T2 MRI (0-5%/6-33%/34-66%/67-100%; adapted from the VASARI [Visually AcceSAbLe Rembrandt Images] MR features for gliomas (20))
- Meningioma volume using the ABC/2 formula on contrast-enhanced T1-weighted MRI/CT: (A) maximum meningioma diameter on axial plane, (B) diameter perpendicular to (A) and (C) maximum height on coronal/sagittal plane, not taking into the account the dural tail
- Meningioma location classed into non-skull base and skull base and further subcategorised according to the ICOM (International Consortium on Meningioma) classification system (Appendix 2)
- Proximity to major dural venous sinuses (superior sagittal sinus/transverse sinus/sigmoid sinus/cavernous sinus/the confluence of sinuses) categorised as separate (within 10 mm), in direct contact with its wall, or invading, excluding the dural tail (Figure 2)
- Contact with critical neurovascular structures (i.e. internal carotid artery and optic apparatus)

Meningiomas that fulfil one of the two previous categories are said to be in proximity to critical neurovascular structures. A video manual prepared by the study team will be made available to assist with standardisation and quality assurance of scan interpretation across participating centres.

[figure not shown]

Figure 2. (A-C) T2 MR axial sequences showing the 3 levels of tumour intensity (circle). (A) Hypointense. (B) Isointense. (C) Hyperintense. (D-F) T1-weighted MR with gadolinium (contrast) showing the relationship between the meningioma and the nearby venous sinus (SSS). (D) Separate as there's no clear attachment to the sinus wall. (E) In direct contact with the lateral wall of the sinus. (F) Clear macroscopic distortion and invasion of the sinus.

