3.10.2. Model recalibration

If calibration and discrimination measures of external validation demonstrate a poor fit, the model will be recalibrated and adjusted using the data of included patients. This will be done over four stages:

- Stage 1: The regression coefficients (including the intercept and slope) will be recalibrated. This will be done using a logistic regression model fitted with the linear predictor as the only covariate.
- Stage 2: The recalibrated model predictors will each be removed in a stepwise manner by a non-automated criterion-based procedure starting with the variable with a hazard ratio closest to 1. After removal of this variable, the aforementioned measures of discrimination of calibration and discrimination will be reassessed to detect model improvement. If the performance of the model is unimproved or worsens, the variable will be reintroduced to the model. This step will be repeated in a staged manner until no further improvements are detected. Introduction of new predictive variables will not be possible as data points captured in this study have been limited to predictive parameters and outcomes as per the IMPACT model.
- Stage 3: The internal validity of the updated model will be assessed using a bootstrapping method
- Stage 4: Adjusted stratification by ACCI and PS (Table 1) will be performed to achieve statistically significant differences in equality across cumulative incidence rate groups, judged by the Fine and Gray test

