If yes, which	Dropdown list/check box 
 • Internal carotid artery • Basilar artery • Vertebral artery • Middle cerebral artery • Anterior cerebral artery • Posterior cerebral artery • Optic apparatus (optic nerve and chiasm) • Trigeminal nerve • Facial nerve • Vestibulo-cochlear nerve • Other 	Prompt entry if previous option (In contact with critical neuro-vascular structures?) has been ticked
Major axis (mm)	Free field	Required entry Note to data collector: In mm to 1 dp. Measure on axial T1/CT + GAD
Minor axis (mm)	Free field	Required entry Note to data collector: In mm to 1 dp. Perpendicular to the major axis on axial T1/CT + GAD
Cor/sag major axis	Free field	Require entry Note to data collector: In mm to 1 dp. Maximum height
Location	Dropdown list/Check box 
 • Convexity 	Required entry. Allow one option only Note to data collector: as per ICOM classification (appendix 2)

	
 • Parasagittal • Parafalcine • Sphenoid wing • Anterior midline • Post fossa-midline • Post fossa-lateral & posterior • Tentorial • Intraventricular • Pineal region 	
Location subcategory	Dropdown list/Check box 
 • Anterior • Posterior • Falco-tentorial • Lateral • Medial (including ACP) • Cribriform plate/olfactory groove • Planum • Tuberculum/diaphragma sellae • Clival • Petro-clival • Anterior foramen magnum • Petrous • Squamous occipital • Posterior foramen magnum • Supratentorial • Infratentorial 	Required entry. Allow one option only Note to data collector: ICOM classification (appendix 2) Appropriate subcategories will appear based on main category selected
Side	Dropdown list/check box 
 • Right • Left • Midline 	Required entry. Allow one option only
MANAGEMENT DECISION (PAGE/SECTION 4)		
Decision	Dropdown list/Check box	Required entry. Allow one option only

	
 • Active monitoring • Surgery • SRS • fRT • Discharge from outpatient care • Lost to follow-up • Dead 	Note to data collector: You will be directed to the relevant page/section dependent on the choice. If the patient died or was lost to follow-up after this point in time, please choose one of the last two options, albeit the intention might have been to continue monitoring or intervene.
ACTIVE MONITORING (SECTION/PAGE 5)		
Scan date	DD/MM/YYYY	Required entry

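### Stage 2 of the model update ranks predictors by a unit-dependent hazard ratio and selects by hand without a decision rule; a Stage 3 bootstrap of the final model alone would miss the selection optimism

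*Protocol*

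**What the plan says.** Protocol Section 3.10.2 comes into play only if the external validation shows that IMPACT fits poorly. It then sets out four stages.

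- **Stage 2, order.** Predictors are "removed in a stepwise manner by a non-automated criterion-based procedure starting with the variable with a hazard ratio closest to 1".
- **Stage 2, keep or drop.** After each removal, calibration and discrimination are looked at again. "If the performance of the model is unimproved or worsens, the variable will be reintroduced to the model".
- **Stage 2, stopping.** "This step will be repeated in a staged manner until no further improvements are detected".
- **Stage 3.** "The internal validity of the updated model will be assessed using a bootstrapping method".

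The performance measures are those of Section 3.10.1: a calibration plot, the Brier score, the C-statistic, the D-statistic and a time-dependent AUC. The section sets no threshold for improvement and no ranking of the measures.

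Section 1.1 lists the candidate predictors as "meningioma volume, meningioma hyperintensity, peritumoral signal change and proximity to critical neurovascular structures". Section 3.8.2 describes how volume is obtained: "Meningioma volume using the ABC/2 formula on contrast-enhanced T1-weighted MRI/CT". Appendix 1 records the diameters in millimetres ("In mm to 1 dp. Measure on axial T1/CT + GAD"), while the endpoint in Section 3.5.1 uses cubic centimetres ("meningioma volume exceeding 10 cm³"). The protocol gives neither the IMPACT coefficients nor the scale on which volume enters the model (linear, logged or grouped).

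**The concern.** The order of removal rests on a quantity that does not measure importance. The hazard ratio of a continuous predictor moves towards or away from 1 when its unit changes, although data, fit and predictions stay the same. The hazard ratio of a categorical predictor depends on the reference level. A predictor with three or four recorded levels, such as tumour signal or peritumoural signal in Section 3.8.2, has several hazard ratios if it is modelled that way. It is then unclear which of them is to be compared with 1.

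The decision that follows is made by eye, on up to five measures, in the same data that supply the estimates. Nothing says what happens if, for example, the C-statistic rises while the Brier score worsens. Small chance differences can settle the choice.

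The updated model has no further external validation in this plan, so the Stage 3 bootstrap is its only check. A bootstrap corrects for selection only if the selection is repeated in every resample. A by-hand procedure without a decision rule cannot be repeated as it is written. If only the final model is resampled, its corrected performance is somewhat too favourable.

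**Working it through.** **1. The plan's own figure.** Section 3.4 asks for 100 events at a 10% progression risk: 100 / 0.10 = 1000 patients. This reproduces. The inflated minimum of 1500 would give 1500 × 0.10 = 150 events. Neither figure is disputed. The simulations below use 1000 patients and 10% events.

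**2. Units.** If the hazard ratio per cm³ is HR, then per k cm³ it is HR^k, and 1 mm³ is 0.001 cm³. The starting values are assumptions.

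| Assumed HR per cm³ | per mm³ | per 5 cm³ | per 10 cm³ |
|---|---|---|---|
| 1.10 | 1.10^0.001 = 1.0001 | 1.10^5 = 1.61 | 1.10^10 = 2.59 |
| 1.30 | 1.30^0.001 = 1.00026 | 1.30^5 = 3.71 | 1.30^10 = 13.8 |

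Against a binary predictor with HR 1.5, a volume effect of 1.10 per cm³ is closer to 1 when expressed per cm³ or per mm³, and further from 1 when expressed per 5 cm³. The order reverses although nothing about the tumour or the model has changed.

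**3. Does the order decide what is lost?** Stage 2 was simulated in a Cox model with four predictors (60 datasets per scenario). The predictor with the hazard ratio closest to 1 was taken out, left out only if the apparent C-statistic rose, and otherwise put back.

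- Volume at 1.3 per cm³, other predictors at 1.5 to 2: volume was tried first in 70% (cm³), 100% (mm³) and 0% (10 cm³) of datasets. It was finally dropped in 0% under all three units.
- Volume at 1.1 per cm³: finally dropped in 3 to 12%.
- All predictors weak (1.1 to 1.2): volume dropped in 10%.

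Units therefore govern which predictor is tried first. The reintroduction rule protects a strong predictor, and a weak one less well.

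**4. Optimism missed by the bootstrap.** Thirty resamples per dataset, first with the chosen predictors held fixed, then with Stage 2 repeated in each resample.

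| Scenario (assumed HRs; volume per cm³, then the other three) | Unit used for ranking | Any predictor dropped | Optimism in C, fixed | Optimism in C, repeated | Difference |
|---|---|---|---|---|---|
| 1.3; 2, 2, 1.1 | cm³ | 32% | 0.0089 | 0.0120 | 0.0031 |
| 1.3; 2, 2, 1.1 | mm³ | 38% | 0.0084 | 0.0115 | 0.0031 |
| 1.1; 2, 2, 1.5 | mm³ | 17% | 0.0122 | 0.0157 | 0.0035 |
| 1.1; 1.2, 1.2, 1.1 | cm³ | 67% | 0.0228 | 0.0313 | 0.0085 |

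The missed share is 0.0031/0.0120 = 26%, 0.0031/0.0115 = 27%, 0.0035/0.0157 = 22% and 0.0085/0.0313 = 27%. Every predictor had a real effect in these data, yet some predictor was dropped in 17 to 67% of datasets. The directly simulated true optimism has a standard error of about 0.004, too imprecise to rank the two approaches. Only the paired contrast of fixed against repeated is informative. These runs used one programmed criterion (C). Free choice between several measures was not simulated.

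**The case against.** There is a good case that little harm follows.

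- **Reintroduction.** A reader might infer that the update will lose volume because of its unit. The documents do not support this: a predictor returns unless performance improves, and in the simulations a strong volume effect was never lost under any unit. This part of the objection stands.
- **Scale of volume.** The protocol does not say that volume is a continuous term. If IMPACT groups it, the unit problem becomes one of reference level. This stands too, and the unit illustration is conditional on it.
- **Bootstrap.** A reader might infer that Stage 2 cannot be repeated in the bootstrap. Stage 3 does not exclude repetition. The word non-automated may mean only that no software stepwise routine is used, and a version with one stated criterion ran without difficulty. Details of the resampling may also sit in a statistical analysis plan that is not shown, and Section 3.10.3 promises a review before the final analysis. So silence about repetition is not an error in itself. What remains is that the protocol does fix the ordering rule and the by-hand selection, and these cannot be replayed until a decision rule is added.
- **Size.** A bootstrap of the final model alone still captured roughly three quarters of the optimism. This stands for the simulated cases, with the reservation that subjective choice between measures could add to the missed part.

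**Conclusion.** The point holds in a limited form. Distance of the hazard ratio from 1 is a poor stated criterion, because it depends on unit or reference level. Selection by hand on several measures in the same data has no rule for disagreement. A bootstrap restricted to the final model would leave selection optimism uncorrected, by about 0.003 to 0.009 in C. That size rests on assumed hazard ratios and an assumed volume distribution, 1000 patients with 10% events, and a single programmed criterion. It is not an estimate for this cohort.

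A reader might go further and infer that the study's main result is compromised. It is not: Stage 2 runs only after poor fit has been found and serves a secondary objective, so the external validation in Section 3.10.1 is unaffected. Nor do the documents show that the updated model's performance will be materially overstated. The change is worth making because it is cheap and because the bootstrap is the updated model's only check.

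**What to change.** Replace the Stage 2 rule in one of two ways.

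1. **No elimination.** Keep all four predictors and choose between re-estimating the baseline, adding a calibration slope, and re-estimating the coefficients, for example by likelihood-ratio test.
2. **Elimination by one criterion.** Name in advance a single unit-free criterion and its threshold, for example change in AIC or a likelihood-ratio chi-square that tests all levels of a predictor together. Use it for both the order and the keep-or-drop decision. Report the other performance measures without letting them decide. State the scale on which volume enters.

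In either case, program all updating steps and say in Stage 3 that they are repeated in every bootstrap sample, so that the corrected performance belongs to the whole procedure and not only to the model it ended with.

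The cost is a change of wording, modest programming and slightly less favourable optimism-corrected figures. No additional data are needed.

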3.10.3. Additional analyses

We envisage that imaging protocols in the participating centres are varied and non-standardised and thus, the growth rate for each meningioma will be determined using a joint longitudinal and event-time outcomes model which does not require regularly spaced time points, and adjusts for informative follow-up, assuming a different intercept and slope for each meningioma (25, 26). The sum of the regression coefficients of random and fixed effects for the slope estimated from the linear model will best represent the average growth rate for each meningioma. Absolute growth rate (AGR) will be defined as the increase in volume per year in cm³ whereas relative growth rate (RGR) will be defined as the percentage increase in volume per year.

Demographic differences across management and outcome groups will be explored with the χ^2 test for categorical variable and the Mann-Whitney U test or Student's t-test for continuous variables. Correlation between baseline variables will be evaluated using the Pearson correlation coefficient. Normally distributed continuous variables will be expressed as mean (standard deviation [SD]) whereas skewed variables as median (interquartile range [IQR]). Differences will be considered statistically significant at $P < 0.05$.

This statistical analysis plan will be reviewed prior to the final analysis of the study.

3.10.4. Health economic analysis

The health economic analysis will adopt the perspective of the National Health Service in the UK. Costs related to clinic appointments and MRI scans will be calculated for the study cohort's retrospectively performed follow-up plans and compared against two follow-up regimes:

- The follow-up regime proposed by the National Institute for Health Care Excellence (NICE) of 2 scans at 12 months and 5 years
- The follow-up regime using the IMPACT model, stratified by risk of progression

4 ETHICS AND DISSEMINATION

4.1. Study registration

It will be the responsibility of the research team at each unit to register the study as a clinical audit with their hospital's audit department, including Caldicott guardian or Information Governance approval as required.

4.2. Local investigator responsibilities

The investigator will be responsible for the overall conduct of the study at the site and compliance with the protocol. Responsibilities may be delegated to an appropriate member of the local research team. The Investigator must also be familiar with the protocol and the study requirements and it is their responsibility to ensure that all staff assisting with the study are adequately informed about the protocol and the study requirement. The Principal Investigator at each centre is responsible for the quality of the data recorded in the database.

4.3. Confidentiality and data protection

No patient identifiable information will be uploaded or stored on the REDCap database. The clinical team can only view the records of patients from their own centre. All records must be identified in a manner designed to maintain patient confidentiality and must be kept in a secure storage area with limited access; all local investigators will store a copy of the link between the patient's unique study number and their patient identifiers on a secure

password protected computer, using a blank link file provided by the study team. The investigator and local research terms involved with this study may not disclose or use for any purpose other than performance of the study, any data, record, or other unpublished, confidential information. They also must comply with the requirements of the Data Protection Act 2018 and GDPR with regard to the collection, storage, processing, and disclosure of personal information. Access to collated patient data will be restricted to individuals from the research team and representatives of the sponsor. Computers used to collate the data will have limited access measures via usernames and passwords. Published results will not contain any personal data that could allow identification of individual patients.

4.4. Ownership

Ownership of the complete dataset arising from this study resides with the steering committee (named in this protocol). Local data collected as part of this study belongs to the local team collecting that data. However, individual clinicians must not submit any part of their individual data for publication or presentation without prior consent from the study research team. Individual participant data, after deidentification, will be made available to researchers whose proposed use of the data is approved by the original study investigators. Proposals should be directed to the primary investigator.

4.5. Dissemination of results

The study results will be reported using the TRIPOD (Transparent Reporting of a multivariable prediction model for Individual Prognosis Or Diagnosis) checklist. The results of this study will be presented at national and international meetings and will be submitted for publication in peer-reviewed journals.

4.6. Authorship eligibility

The list of named authors will encompass the study's steering committee. The contribution of all investigators, will be recognised with PubMed Citable collaborator-status authorship under the umbrella of the IMPACT study investigators.

5 FUNDING

No funding has been sought for the completion of this project. Certain elements of this study will be covered by funding received by the Chief Investigator ([name]) from The Brain Tumour Charity.

6 STUDY TIMELINE

Activity	Up to Jul-20	Aug-20	Sep-20	Oct-20	Nov-20	Dec-20	Jan-21	Feb-21 - Jul-21	Aug-21 - Oct-21	Nov-21	Dec-21
Arrange REDCap access											
Build REDCap database, phase 1											
Build REDCap database, phase 2											
Recruit centres											
Local audit approval											
Identification of patients											
Data collection											
Data processing and analysis											
Results presentation											
Publication of report											
	Completed										
	Ongoing										
	On hold										

7 CONCLUSION

This study will be the first international multicentre study collecting data on outcomes of management of incidental asymptomatic meningioma which will enable validation of the IMPACT prognostic model and from the basis of ongoing prospective and economic studies.

9 APPENDICES

9.1. Appendix. 1. Guide for REDCap database developers

Characteristic	Options	Notes
BASELINE CLINICAL CHARACTERISTICS (PAGE/SECTION 1)		
Age (years)	Free field	Required entry
Sex	Dropdown list/check box 
 • Male • Female 	
Ethnicity	Dropdown list/check box 
 • White • Mixed / Multiple ethnic groups • Asian / Asian British • Black / African / Caribbean / Black British • Other ethnic group • NA 	Required entry. Allow one option only. Other ethic group prompts a free text box
Comorbidities	Check box 
 • Hypertension - systolic > 140 or diastolic > 90 and patients on medical treatment • Previous myocardial infarction • Congestive heart failure • Peripheral vascular disease • Previous stroke/TIA - If hemiplegia present, do not check • Hemi/paraplegia • Diabetes which requires medical treatment 	Required entry. Allow multiple options. Note to data collector: Age and comorbidities will be used to calculate the age adjusted Charlson comorbidity index. Each of these is defined in the guide provided

	
 • Diabetes with end-organ damage - if so, do not check diabetes that requires treatment • COPD/Asthma • Renal disease • Mild liver disease - Hep B/C or cirrhosis without portal hypertension • Moderate to severe liver disease - cirrhosis with portal hypertension, jaundice, ascites • Peptic ulcer disease • Cancer - excluding basal cell carcinoma • Metastatic cancer - if so, do not check cancer • Rheumatic or connective tissue disease • HIV/AIDS • Skin ulcers/cellulitis • Depression • Dementia • On Warfarin 	
WHO Performance status	Dropdown list/check box 
 • 0 • 1 • 2 • 3 • 4 	Required entry. Allow one option only
Indication for scan	Dropdown list/check box 
 • Headache • Cerebrovascular accident • Head injury • Audiovestibular symptoms 	Required entry. Allow multiple options. Note to data collector: The meningioma must not be thought to be the cause of these symptoms. Other indications might include lethargy, research, sinusitis, anosmia...etc. Other prompts a free text box

	
 • Visual symptoms • Psychiatric symptoms • Cognitive symptoms • Loss of consciousness • Other 	
NUMBER OF MENINGIOMAS ON 1ST DIAGNOSTIC SCAN (PAGE/SECTION 2)		
Initial scan date	DD/MM/YYYY	Required entry. YYYY can't be ≤2007 or ≥2011
How many meningiomas?	Check box 
 • Single • Multiple 	Required entry If a single meningioma, direct to section/page 3. If multiple, prompt a new entry point (e.g. check box with options being 2-6) with number of meningiomas present. Each meningioma will then be treated as a separate entity with regards to the upcoming sections.
BASELINE IMAGING CHARACTERISTICS (SECTION/PAGE 3)		
Meningioma signal intensity on T2	Dropdown list/check box 
 • Hypointense • Hyperintense • Isointense • NA 	Required entry. Allow one option only Note to data collector: In relation to the contralateral grey matter. If only baseline CT available, NA
Meningioma signal intensity on FLAIR	Dropdown list/check box 
 • Hypointense • Hyperintense • Isointense • NA 	Required entry. Allow one option only Note to data collector: In relation to the contralateral grey matter. If only baseline CT available, NA
Peritumoural signal intensity on T2	Dropdown list/check box 
 • 0-5% • 6-33% • 34-66% • 67-100% • NA 	Required entry. Allow one option only Note to data collector: In relation to tumour volume. If only baseline CT available, NA
Peritumoural signal intensity on FLAIR	Dropdown list: 
 • 0-5% • 6-33% • 34-66% • 67-100% • NA 	Required entry. Allow one option only Note to data collector: In relation to tumour volume. If only baseline CT available, NA
Venous sinus nearby	Checkbox	Required entry.

		Note to data collector: Tick box if within 10 mm, in direct contact or invading one of: superior sagittal sinus (SSS), sigmoid sinus (SS), transverse sinus (TS), cavernous sinus (CS) and the confluence of sinuses (CoS)
If yes, specify	Dropdown list/check box 
 • Superior sagittal sinus • Cavernous sinus • Sigmoid sinus • Transverse sinus • Confluence of sinuses 	Prompt entry if previous option (venous sinus nearby) has been ticked. Allow one option only.
Separate, direct contact or invaded?	Dropdown list/check box 
 • Separate • Direct contact • Invaded 	Prompt entry if previous option (venous sinus nearby) has been ticked. Allow one option only
In contact with critical neuro-vascular structures?	Checkbox	Required entry
If yes, which	Dropdown list/check box 
 • Internal carotid artery • Basilar artery • Vertebral artery • Middle cerebral artery • Anterior cerebral artery • Posterior cerebral artery • Optic apparatus (optic nerve and chiasm) • Trigeminal nerve • Facial nerve • Vestibulo-cochlear nerve • Other 	Prompt entry if previous option (In contact with critical neuro-vascular structures?) has been ticked
Major axis (mm)	Free field	Required entry Note to data collector: In mm to 1 dp. Measure on axial T1/CT + GAD
Minor axis (mm)	Free field	Required entry Note to data collector: In mm to 1 dp. Perpendicular to the major axis on axial T1/CT + GAD
Cor/sag major axis	Free field	Require entry Note to data collector: In mm to 1 dp. Maximum height
Location	Dropdown list/Check box 
 • Convexity 	Required entry. Allow one option only Note to data collector: as per ICOM classification (appendix 2)

	
 • Parasagittal • Parafalcine • Sphenoid wing • Anterior midline • Post fossa-midline • Post fossa-lateral & posterior • Tentorial • Intraventricular • Pineal region 	
Location subcategory	Dropdown list/Check box 
 • Anterior • Posterior • Falco-tentorial • Lateral • Medial (including ACP) • Cribriform plate/olfactory groove • Planum • Tuberculum/diaphragma sellae • Clival • Petro-clival • Anterior foramen magnum • Petrous • Squamous occipital • Posterior foramen magnum • Supratentorial • Infratentorial 	Required entry. Allow one option only Note to data collector: ICOM classification (appendix 2) Appropriate subcategories will appear based on main category selected
Side	Dropdown list/check box 
 • Right • Left • Midline 	Required entry. Allow one option only
MANAGEMENT DECISION (PAGE/SECTION 4)		
Decision	Dropdown list/Check box	Required entry. Allow one option only

	
 • Active monitoring • Surgery • SRS • fRT • Discharge from outpatient care • Lost to follow-up • Dead 	Note to data collector: You will be directed to the relevant page/section dependent on the choice. If the patient died or was lost to follow-up after this point in time, please choose one of the last two options, albeit the intention might have been to continue monitoring or intervene.
ACTIVE MONITORING (SECTION/PAGE 5)		
Scan date	DD/MM/YYYY	Required entry
Peritumoural signal intensity on T2	Dropdown list/check box 
 • 0-5% • 6-33% • 34-66% • 67-100% • NA 	Required entry. Allow one option only Note to data collector: In relation to tumour volume on T2/FLAIR MRI. If only CT or T1 MRI available, NA
Peritumoural signal intensity on FLAIR	Dropdown list/check box 
 • 0-5% • 6-33% • 34-66% • 67-100% • NA 	Required entry. Allow one option only Note to data collector: In relation to tumour volume on FLAIR MRI. If only CT or T1 MRI available, NA
Venous sinus nearby	Checkbox	Required entry. Note to data collector: Tick box if within 10 mm, in direct contact or invading one of: superior sagittal sinus (SSS), sigmoid sinus (SS), transverse sinus (TS), cavernous sinus (CS) and the confluence of sinuses (CoS)
If yes, specify	Dropdown list/check box 
 • Superior sagittal sinus • Cavernous sinus • Sigmoid sinus • Transverse sinus • Confluence of sinuses 	Prompt entry if previous option (venous sinus nearby) has been ticked. Allow one option only
Separate, direct contact or invaded?	Dropdown list/check box 
 • Separate • Direct contact • Invaded 	Prompt entry if previous option (venous sinus nearby) has been ticked. Allow one option only

Any new meningioma-related symptoms?	Checkbox	Required entry
If yes, specify domain	Dropdown list/check box 
 • Seizure • Headache • Motor • Sensory • Language • Cognitive • Other 	Prompt entry if previous option (Any new meningioma-related symptoms?) has been ticked. Allow multiple options
Major axis (mm)	Free field	Required entry Note to data collector: In mm to 1 dp. Measure on axial T1/CT + GAD if available
Minor axis (mm)	Free field	Required entry Note to data collector: In mm to 1 dp. Perpendicular to the major axis on axial T1/CT + GAD if available
Cor/sag major axis (mm)	Free field	Required entry Note to data collector: In mm to 1 dp. Maximum height
Outcome	Dropdown list/check box 
 • Resume follow-up (active monitoring) • Surgery • SRS • fRT • Discharge • Lost to follow-up • Dead 	Required entry. Allow one option only Note to data collector: You will be directed to the relevant page/section dependent on the choice. If the patient died or was lost to follow-up after this interval scan, please choose one of the last two options, albeit the intention might have been to continue monitoring or intervene. If the option you choose is set to take place in the future, choose the option, save the data entered and exit the form with no further information required.
SURGERY (SECTION/PAGE 6)		
Surgery date	DD/MM/YYYY	Required entry
Indication for intervention	Dropdown list/checkbox 
 • Clinical-radiological • Clinical • Radiological • Patient preference 	Required entry. Allow one option only
Preoperative WHO PS	Dropdown list/checkbox 
 • 0 • 1 	Required entry. Allow one option only

	
 • 2 • 3 • 4 	
Preoperative comorbidities	
Check box
 
 • Hypertension - systolic > 140 or diastolic > 90 and patients on medical treatment • Previous myocardial infarction • Congestive heart failure • Peripheral vascular disease • Previous stroke/TIA - If hemiplegia present, do not check • Hemi/paraplegia • Diabetes which requires medical treatment • Diabetes with end-organ damage - if so, do not check diabetes that requires treatment • COPD/Asthma • Renal disease • Mild liver disease - Hep B/C or cirrhosis without portal hypertension • Moderate to severe liver disease - cirrhosis with portal hypertension, jaundice, ascites • Peptic ulcer disease • Cancer - excluding basal cell carcinoma • Metastatic cancer - if so, do not check cancer 	
Required entry. Allow multiple options.
 
Note to data collector: Age and comorbidities will be used to calculate the age adjusted Charlson comorbidity index. Each of these is defined in the guide provided

	
 • Rheumatic or connective tissue disease • HIV/AIDS • Skin ulcers/cellulitis • Depression • Dementia • On Warfarin 	
Simpson grade	Dropdown list/check box 
 • 1-GTR • 2-GTR • 3-GTR • 4-STR • 5-STR 	Required entry. Allow one option only
WHO grade at the time of surgery	Dropdown list/check box 
 • 1 • 2 • 3 	Required entry. Allow one option only Note to data collector: According to the WHO classification at the time of surgery
Microscopic brain invasion	Dropdown list/check box 
 • Yes • No • Brain tissue absent • NA 	Required entry. Allow one option only Note to data collector: as described in the pathology report.
Updated WHO grade (2016)	Dropdown list/check box 
 • 1 • 2 • 3 • NA 	Required entry. Allow one option only. Only to appear if date of surgery <2017 Note to data collector: For meningiomas operated prior to 2016, grading will have been done according to the 2007 classification. The 2016 version can upgrade WHO grade 1 meningiomas to grade 2 if microscopic brain invasion is present. This means that WHO grade 2 and 3 meningiomas remain unchanged. Grade 1 meningiomas on the other hand can be upgraded in the presence of brain invasion. This requires review by a pathologist and so if not feasible, choose NA. For meningiomas classed according to the 2016 WHO classification, grade remains unchanged.
Postoperative surgical complications	Checkbox	Required
Complication	Dropdown list/check box 
 • Haemorrhage • Hydrocephalus 	Prompt entry if previous option (Postoperative surgical complications) has been ticked Allow more the one option

	
 • Surgical site infection - superficial and deep incisiona • Surgical site infection - intracranial (meningitis, ventriculitis and abscess) • Stroke • CSF leak • Other 	
New or worsening neurological impairment	Checkbox	Prompt entry if previous option (Postoperative surgical complications) has been ticked Note to data collector: If symptoms present tick box. Note that some patients will have a radiological haemorrhage on postoperative imaging with no symptoms. Include these but don't tick clinical manifestation. On the other hand, some patients will have new symptoms such as seizure with no radiological cause, include these as well.
Clinical manifestation	Dropdown list/checkbox 
 • Seizure • Headache • Motor • Sensory • Language • Cognitive • Reduced GCS • Other 	Prompt entry if previous option (New or worsening neurological impairment) has been ticked. Allow multiple options
Pharmacological intervention	Checkbox	Prompt entry if previous option (Postoperative surgical complications) has been ticked
Surgical intervention	Dropdown list/checkbox 
 • No • Without GA • Under GA 	Prompt entry if previous option (Postoperative surgical complications) has been ticked
ICU admission	Checkbox	Prompt entry if previous option (Postoperative surgical complications) has been ticked
Organ failure	Dropdown list/checkbox 
 • None • Single-organ • Multi-organ 	Prompt entry if previous option (Postoperative surgical complications) has been ticked. Allow one option only
Persisted with no improvement beyond 30 days?	Checkbox	Prompt entry if previous option (Postoperative surgical complications) has been ticked

Postoperative medical complications	checkbox	Required
Complication	Dropdown list/check box 
 • Myocardial infarction • Arrhythmia • Pneumonia • Pulmonary embolism • Deep venous thrombosis • Urinary tract infection • Acute kidney injury • Other 	Prompt entry if previous option (Postoperative medical complications) has been ticked Allow more than one option
Pharmacological intervention	Checkbox	Prompt entry if previous option (Postoperative medical complications) has been ticked
Surgical intervention	Dropdown list/checkbox 
 • No • Without GA • Under GA 	Prompt entry if previous option (Postoperative medical complications) has been ticked
ICU admission	Checkbox	Prompt entry if previous option (Postoperative medical complications) has been ticked
Organ failure	Dropdown list/checkbox 
 • None • Single-organ • Multi-organ 	Prompt entry if previous option (Postoperative medical complications) has been ticked. Allow one option only
Persisted with no improvement beyond 30 days?	Checkbox	Prompt entry if previous option (Postoperative medical complications) has been ticked
Postoperative WHO PS	Dropdown list/checkbox 
 • 0 • 1 • 2 • 3 • 4 • 5 (dead) 	Required. Allow one option only
Recurrence	Checkbox	Prompt entry if previous option (Postoperative WHO PS) is not 5
Scan date (at recurrence or last follow-up date if no recurrence)	DD/MM/YYYY	Prompt entry if previous option (Postoperative WHO PS) is not 5
